2 INTRODUCTION

2.1 MICROSCOPIC COLITIS

Microscopic colitis (MC) is a chronic inflammatory bowel disease, characterized by watery, non-bloody diarrhea with macroscopically normal colonic mucosa and typical microscopic features. Other clinical findings of MC may include nocturnal diarrhea, faecal incontinence, abdominal pain and mild weight loss.^{1,2}

No unifying mechanism has been identified as being responsible for the pathophysiological abnormalities found in MC and the disease is likely to have multifactorial causes.³ Several risk factors such as cigarette smoking, especially among young patients,⁴ have been shown to be associated with the increased incidence of the disease. Diversion of the fecal stream has sometimes resulted in histological improvements,⁵ suggesting that the disease is caused by an abnormal response to luminal antigens. A wide variety of drugs have been proposed as potential triggers or etiological factors for MC, but none has been conclusively implicated. These include the non-steroidal anti-inflammatory drugs (NSAIDs), proton pump inhibitors (PPIs), selective serotonin reuptake inhibitors (SSRIs) and statins. However, all these drugs are widely used, therefore, it is expected that patients with MC might frequently use them coincidentally. Some authors point out that drug-induced MC cases are more likely due to an idiosyncratic reaction.^{6,7}

The diagnosis of MC rests on characteristic pathological findings in biopsies from normal or oedematous colonic mucosa. Although the topographic distribution of MC remains controversial, rectal biopsies are not sufficient.^{6,8} Some studies demonstrate that biopsies from the right and transverse colon are necessary for the diagnosis of MC, while others demonstrate that biopsies from the descending and sigmoid colon suffice for diagnosing this disease.⁸⁻¹² However, colonoscopy should be preferred because it is essential to rule out malignant colonic disease. Diarrhea caused by other diseases should be excluded; these diseases include bile acid diarrhea, coeliac disease, and lactose malabsorption.¹³

Two distinct histological types of MC, lymphocytic colitis (LC) and collagenous colitis (CC), have been described, but overlapping features are often present; indeed, some authors think that LC and CC are two histological subtypes of the same disease.^{3,14}

Abnormal chronic inflammation in the lamina propria is a typical histological characteristic but does not allow a distinction between the subtypes of MC.¹⁵ CC is characterized by a thickened subepithelial collagen layer, i.e., $> 10 \mu\text{m}$ in well-oriented biopsies cut perpendicularly to the surface,¹⁶ and lymphocytic colitis (LC) is characterized by an increased number of intraepithelial lymphocytes (IEL), i.e., ≥ 20 IEL per 100 epithelial cells. Colonic biopsies are considered normal in the absence of chronic inflammation in the lamina propria, when the number of surface epithelial cells is ≤ 5 IEL/100, and the collagen band is ≤ 5 micrometers.^{10,17}

Recent studies have shown that histological features in the individual patient are inconsistent over time, as findings of MC interchange with chronic (non-specific) inflammation or incomplete signs of MC at prior or repeat colonoscopy, and the overlap between CC and LC is significant.^{8,18,19} This histological interchange between MC subtypes and the incomplete identification of some patients have led to the introduction of a third subtype designated as incomplete MC (IC). The histological criteria for IC are an abnormally thickened collagenous band (> 5 and $< 10 \mu\text{m}$), and /or an increased number of intraepithelial lymphocytes (> 5 and < 20 per 100 epithelial cells) without reaching the thickness or number required for the diagnosis of CC or LC.¹

Epidemiologic studies show that MC is almost as common as classic IBD (i.e. Crohn's disease and ulcerative colitis).^{13,20-22} The incidence of MC appears to be rising and in some countries it may be diagnosed in 10% of patients investigated for chronic non-bloody diarrhoea, and in 20% or more of such patients older than 70 years.^{13,20} After a period of rising incidence figures, the data have been more divergent in recent studies. Incidence rates of 2.6/100,000 to 10.8/100,000 inhabitants have been reported for CC, and an annual incidence rate of 2.2 to 14 per 100,000 inhabitants for LC.^{13,20-22} Patients with MC are predominantly elderly women, and the average age at diagnosis is approximately 65 years, but a recent study shows that the age at diagnosis is increasing and a large proportion are now diagnosed in their seventies. This may be attributable to the rising of life expectancy observed over the last decades.²³ The female predominance is very clear in MC, but is less pronounced for LC than for CC.²¹

The incidence of IC has been described in only one consecutive case series in which a seven-fold increase was found for both IC and LC from 1999-2001 to 2008-2010 as compared to a 3-fold increase for CC.²⁴

2.2 BIOMARKERS IN MICROSCOPIC COLITIS

Given the invasive nature of endoscopy, the implementation of an easy, non-invasive method to support the pre-diagnostic screening and monitoring of disease activity is essential.

An increased prevalence of autoimmune serological tests has been found in MC patients but no clinically useful marker for the disease has yet been identified.³

The faecal markers evaluated so far in MC include a variety of substances/proteins that either leak from or are generated by the inflamed mucosa in the gut. Proteins studied include lactoferrin, myeloperoxidase (MPO), calprotectin, eosinophil cationic protein (ECP) and eosinophil protein X (EPX), as indicators of neutrophilic, macrophage and eosinophil activation. Likewise, studies of tryptase, occult blood and cytokines have been performed.²⁵ Faecal calprotectin has been shown to be useful in the diagnosis of IBD, correlates with mucosal disease activity and can help to predict response to treatment or relapse. In IBD, the presence of active gut inflammation is associated with migration of leucocytes, including neutrophils, to the gut mucosa.²⁶ As a result the faecal stream contains increased levels of these inflammatory proteins including calprotectin. Faecal calprotectin has been shown to differentiate quiescent from active disease in both patients with CD and UC.^{27,28}

Overall, 52 patients with MC have been investigated for faecal calprotectin in five different studies, of whom 71% (n=37) had positive samples.²⁹⁻³³ In two cohorts calprotectin was significantly increased compared to healthy controls and decreased significantly when remission was induced. On the other hand, in the two studies no correlation was found between calprotectin levels and disease activity (measured by bowel frequency), stool consistency and histological grade of inflammation in mucosal biopsies.^{32,33}

Overall ECP and EPX have been examined in 15 and 33 patients with active CC, respectively.^{32,34,35} In the study of Lestejo et al., 2006, 18 patients with CC were compared with patients with IBDs and healthy controls in order to elucidate whether EPX in combination with other faecal markers could be used to distinguish between these disorders. Eleven patients (61%) had EPX values above the upper limit of normal, and values were significantly higher than in IBDs and healthy controls.³⁴

In the study of Wagner et al., 2011, ECP and EXP were positive in 11 and 8 out of 12 patients with active CC disease, respectively, and became normal in all patients when remission was induced with budesonide.³²

In spite of the small samples analyzed, ECP and EXP may be promising faecal markers.³⁶

The association of faecal calprotectin, ECP and EXP with clinical and histological features in MC patients will be explored in this study.

2.3 RATIONALE

There's a lack of epidemiological data regarding MC in Portugal, including its incidence, prognosis factors and therapies used to treat this condition. Therefore, it becomes pertinent to characterize this population and, simultaneously, evaluate the key characteristics that distinguish this clinical entity from other conditions among a population who attends a gastroenterology setting with symptoms of chronic watery diarrhea. An observational study using sound epidemiological methods can provide valuable information regarding these aspects.

This study aims to estimate the prevalence of MC and its subtypes among patients who attend to the gastroenterologist appointment due to chronic, watery diarrhea of unknown etiology and who are eligible to colonoscopy. In addition, socio-demographic, clinical characteristics and treatment patterns will be described for patients with confirmed diagnosis of MC and these features will be compared with non-MC cases. Furthermore, this study will prospectively assess the clinical and histological progression of MC patients during a follow up period of 2 years. Potential biomarkers for this condition will also be explored.

No research hypothesis is predefined.

3 OBJECTIVES

3.1 PRIMARY OBJECTIVE

To determine the prevalence of microscopic colitis (MC) among patients who attend a specialist appointment with symptoms of chronic, watery diarrhea of unknown etiology for more than 4 weeks and undergo colonoscopy.

3.2 SECONDARY OBJECTIVES

- To determine the prevalence of MC subtypes (CC, LC and IC)
- To compare the socio-demographic, clinical and histological characteristics and previous therapies of patients with confirmed diagnosis of MC (MC patients) versus patients without diagnosis of MC (non-MC patients)
- To describe the therapeutic attitude regarding MC patients over a period of 24 months
- To describe the clinical activity of MC patients over a period of 24 months.
- To describe the histological features of MC patients 24 months after diagnosis.
- To explore the association of socio-demographic, clinical and histological characteristics with clinical activity among MC patients followed for 24 months.
- To explore the association of socio-demographic, clinical characteristics with histological activity among MC patients followed for 24 months.
- To explore the correlation between the treatments used by MC patients and clinical activity.
- To explore the correlation between the treatments used by MC patients and histological activity.

- To explore the correlation between fecal calprotectin, EPC and EPX levels and clinical activity among MC patients.
- To explore the correlation between fecal calprotectin, EPC and EPX levels and histological activity among MC patients.

4 STUDY DESIGN

This is a multicenter, cross-sectional, observational study aiming to determine the prevalence of MC among a consecutive sample of subjects who attend a specialist consultation with symptoms of chronic watery diarrhea. In addition, the study design contemplates a 24-month prospective component with repeated measures for all patients with confirmed diagnosis of MC.

There is no imposed experimental intervention or treatment in this study. All therapeutic decisions and management of subjects will be done according to routine clinical practice.

All subjects who meet eligibility criteria and give their written informed consent to participate will be consecutively enrolled and characterized regarding several socio-demographic and clinical characteristics of interest. All eligible subjects will undergo a colonoscopy according to the routine practice for this type of population (Figure 1). Colonic specimens from all segments will be collected for subjects with macroscopically normal colonoscopies as part of the differential diagnosis of MC. Subjects with abnormal findings in colonoscopy suggestive of disorders other than MC will not be included in the prospective component of the study. These patients will continue to be managed according to the center's routine procedures.

The subjects with confirmed diagnosis of MC (upon histology assessment) will be followed over a period of 24 months in this study in order to investigate the clinical and histological progression. The data collection time points over this period will reflect this routine schedule. According to previous epidemiological studies on MC, it is estimated that 10-15% of patients with chronic, watery diarrhea will have a confirmed diagnosis of MC.^{23,37}

Patients without confirmed histological diagnosis of MC will not be followed up during the prospective part of the study. These patients will continue to be managed according to the center's routine procedures.

Socio-demographic and clinical characteristics of patients without diagnosis of MC (either based on macroscopic or histological assessment) will be directly compared with MC patients.

Overall, 300 subjects will be included in this study. The recruitment period will last one year but may be extended if the target number of participants is not achieved within the defined timeframe.

A total of 10 centers in Portugal are expected to participate. Subject recruitment will be competitive across participating centers.

The physician should include the eligible patients consecutively as they attend to the consultation.

[figure not shown]

Figure 1 – Study Flowchart

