6 STUDY POPULATION

6.2 INCLUSION CRITERIA

Study subjects must fulfill the following criteria:

1. Patients who signed the informed consent
2. Male or female patients, 18 years or older;
3. Patients with chronic or intermittent, watery diarrhea of unknown etiology for more than 4 weeks
4. Patients who are eligible for complete colonoscopy according to physician's clinical criteria

6.3 EXCLUSION CRITERIA:

Subjects will be excluded if at least one of the following criteria is met:

1. Patients with history of IBDs or any other known intestinal disease.
2. Any condition that precludes the patient to undergo complete colonoscopy.
3. Patients who are being treated with any investigational agent;
4. Pregnancy
5. Patients who are not willing to comply with routine clinical appointments or procedures.

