7 INFORMATION TO BE COLLECTED

7.1 VARIABLES TO BE CAPTURED

Baseline characteristics

The following socio-demographic, clinical characteristics will be collected for all eligible subjects.

- Date of birth
- Sex
- Height
- Weight
- Smoking status
 - non-smoker: never smoked before or smoked a little occasionally
 - former smoker: patients who had quit smoking more than 6 months before inclusion in the study;
 - current smoker: greater than 7 cigarettes (or approximately half a pack) per week for at least 6 months and had reported any cigarette smoking in the previous 6 months.
- History of bowel surgery
- Familial history of IBDs
- Date of start of first symptoms of diarrhea (at least the month and the year when the patient first experienced non-bloody, watery diarrhea)
- Acute onset of symptoms (yes/no)
- Symptoms (to be captured by the physician by interviewing the patient and referring to the previous 7 days):
 - number of stools per day (the mean number of stools and watery stools per day will be calculated by summing the number of stools [any type] and watery stool that occurred over the week before the time point of assessment divided by 7 days).
 - type of stool (1 to 7 - Bristol Stool Chart)
 - nightly diarrhea
 - urgency (0 = no urgency, 1 = need to defecate within 30 minutes, 2=immediate need to empty the bowel, 3 = fecal incontinence - have to go immediately to the toilette)
 - difficulties staying continent with a respective bowel movement
 - abdominal pain (0 = no pain, 1 = mild, 2 = moderate, 3 = severe pain)
- Unexplained weight loss (> 4.5 kg) in the previous 6 months.
- Comorbidities, including the following conditions of interest: heart disease, hypertension, malignant disease, bile acid malabsorption, celiac disease, rheumatoid arthritis, Diabetes mellitus I, Sjögren's syndrome, Raynaud's syndrome, psoriasis, thyroiditis, hyperthyroidism, hypothyroidism, other auto-immune disorders.
- Pharmacological therapies (within the previous 3 months before study inclusion), including the following therapies of interest: NSAIDs, salicylic acid, proton pump inhibitors, SSRIs and statins.
- Laboratory parameters (prior to colonoscopy) - hemoglobin, platelets, leukocytes, neutrophils, eosinophiles, basophiles, monocytes, lymphocytes, erythrocyte sedimentation rate (ESR), C-reactive protein (CRP), iron and transferrin.
- Fecal sample - for assessment of calprotectin, ECP and EPX levels.

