- Result of colonoscopy: normal/abnormal - describe whether other findings may have caused diarrhoea (e.g., polyps > 2 cm, tumors, Crohn's disease, ulcerative colitis, ischemic colitis, other).

For patients with macroscopically normal colonoscopy:

- Date of sampling of colonic specimens (this date will correspond to the date of MC diagnosis, if confirmed).
- Date of histological assessment
- Histological evidence of MC (yes/no). The following features will be captured:
 - Geboes Index (grade for each of the colon segments: rectum, sigmoid, descending, transverse and ascending) – see Section 7.4.2.
 - Thickness of the subepithelial collagen layer (not observed, $\leq 5 \mu\text{m}$; > 5 and $< 10 \mu\text{m}$; $\geq 10 \mu\text{m}$)
 - IEL in the surface epithelium (not observed, < 5 IEL/100 surface epithelial cells, > 5 and < 20 IEL/100 surface epithelial cells, ≥ 20 IEL/100 surface epithelial cells);
- If a diagnosis of MC was not confirmed, was other diagnosis established? Yes/no - if yes, describe.

Characterization of MC patients

- MC histological assessment: location of microscopic findings (by colon segment), type of MC (lymphocytic, collagenous, incomplete colitis) - see histological assessment in section 7.4.
- Therapeutic attitude upon MC confirmation
 - Antidiarrheal medication (e.g., loperamide or diphenoxylate/atropine),
 - Bismuth subsalicylate or aminosalicylates, e.g. 5-aminosalicylic acid
 - Cholestyramine
 - Corticosteroids (budesonide, prednisolone)
 - Immunosuppressive agents, e.g. azathioprine, 6-mercaptopurine or methotrexate
 - Surgical intervention (e.g. ileostomy)
 - Other interventions (pharmacological or non-pharmacological)
- Dispensing of patient diary card to document the number of stools including the type according to Bristol stool form scale (see section 7.2) in the week prior to the next appointment. In addition, the use of additional pharmacological or other therapies will be recorded by the patient.

Follow up assessments of MC patients (as per routine practice) - month 3, 6, 9, 12, 15, 18, 21 and 24.

The following will be assessed throughout the 24-month prospective component of the study - see **Appendix**.

At every data collection time point

- Weight (kg)
- Symptoms (to be captured by the physician by checking the patient diary and interviewing the patient, referring to the previous 7 days):

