8.2 SECONDARY ENDPOINTS

- Proportion of patients with confirmed diagnosis of each subtype of MC (CC, LC and IC)
- Age, gender, BMI, smoking status, duration of symptoms, stool frequency and consistency (type), familial history of IBDs, comorbidities, previous pharmacological/ non-pharmacological therapies and laboratory parameters to be compared between MC patients and non-MC patients.
- Treatments (pharmacological/non-pharmacological) prescribed by specialist for patients with MC diagnosis
- Number of stools and type (Bristol stool form scale), urgency and abdominal pain over the last 7 days before each time point of assessment for patients with MC diagnosis.
- Proportion of MC patients with clinical remission at each data collection time point (month 3, 6, 9, 12, 15, 18, 21 and 24)
Clinical remission: mean of < 3 stools per day and mean of < 1 watery stool per day
- Proportion of MC patients with histological remission at month 24.
See section 8.3.2 for definition of histological remission
- Age, gender, BMI, smoking status, duration of symptoms, stool frequency and consistency, familial history of IBDs, age at diagnosis of MC, time to diagnosis of MC, comorbidities, pharmacological/non-pharmacological therapies, laboratory parameters and histological features, compared with clinical activity status (active/non active) described for patients with MC diagnosis.
- Age, gender, BMI, smoking status, duration of symptoms, stool frequency and consistency, familial history of IBDs, age at diagnosis of MC, time to diagnosis of MC, comorbidities, pharmacological/non-pharmacological therapies, laboratory parameters, compared with histological features, described for patients with MC diagnosis.
- Area under the ROC curve of fecal calprotectin, ECP and EPX levels with clinical activity at each data collection time points among MC patients.
- Area under the ROC curve of fecal calprotectin ECP and EPX levels with histological activity at each data collection time points among MC patients

For definition of clinical and histological activity see section 8.3.1 and 8.3.2.

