9 STATISTICAL ANALYSIS

9.1 GENERAL CONSIDERATIONS

All quantitative variables will be summarized through descriptive statistics namely mean, median, standard deviation and range (minimum and maximum) and qualitative variables through absolute (n)

and relative frequencies (%) and 95% confidence intervals (if applicable). The statistical analysis will be performed through frequency tables for qualitative variables and tables with descriptive statistics for quantitative variables.

The association between two quantitative variables will be performed through Pearson correlation coefficient or Spearman correlation coefficient, in case the normality assumption is not verified.

The association of two categorical variables will be tested through the Chi-Square test or Fisher Exact test (if applicable).

The comparison of two independent samples in respect to quantitative variables will be performed through t-test for independent samples or the Mann-Whitney non-parametric test, according to the assumption validations of the statistical test (if applicable).

The proportion of patients with clinical remission and histological remission (overall, by MC subtype and colonic segment) at each data collection time points will be summarized using 95% confidence intervals.

Area under the ROC curve will be used to correlate numerical variables with binary categorical variables. A high discriminatory ability will be considered for values > 0.75 .

Repeated Measures Analysis or Generalized Estimated Equations will be used to investigate the evolution profile of clinical and histological characteristics throughout the data collection time points (time-effect).

Generalized Estimated Equations will be used to explore the association between clinical (as independent variable) and histologic features (as dependent variable) observed within-patients.

The association analysis of fecal calprotectin, EPC and EPX with clinical activity

- The association between fecal calprotectin levels EPC and EPX with clinical activity (remission/active disease) will be analyzed through Area Under the ROC Curve at each data collection time point (diagnosis and every 3 months up to month 24).

The association analysis of fecal calprotectin EPC and EPX with histological features

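### The only MC versus non-MC comparison pools patients with visible colonic disease and patients with a normal colon and negative histology, so it cannot show which conditions MC differs from.

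*Protocol*

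**What the plan says.** Protocol section 4 (Study design) fixes the comparator: "Socio-demographic and clinical characteristics of patients without diagnosis of MC (either based on macroscopic or histological assessment) will be directly compared with MC patients". The secondary endpoints in section 8.2 carry the same two-group contrast, ending with "laboratory parameters to be compared between MC patients and non-MC patients". Section 7.1 lists those laboratory parameters; they include hemoglobin, platelets and leukocytes as well as "erythrocyte sedimentation rate (ESR), C-reactive protein (CRP), iron and transferrin".

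An abnormal colonoscopy is recorded under section 7.1 with an instruction to "describe whether other findings may have caused diarrhoea (e.g., polyps > 2 cm, tumors, Crohn's disease, ulcerative colitis, ischemic colitis, other". Section 4 limits what these patients are kept out of: "Subjects with abnormal findings in colonoscopy suggestive of disorders other than MC will not be included in the prospective component of the study". They stay in the cross-sectional comparison. The first exclusion criterion in section 6.3 is "Patients with history of IBDs or any other known intestinal disease", which removes disease that is already known but not disease first found at the study colonoscopy.

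For the analysis, section 9.1 states: "The comparison of two independent samples in respect to quantitative variables will be performed through t-test for independent samples or the Mann-Whitney non-parametric test". Categorical variables get a chi-square or Fisher test. The protocol nowhere splits the non-MC group by colonoscopy result.

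**The concern.** The two parts of the non-MC group are unlike. Section 2.1 describes MC as a disease with macroscopically normal mucosa, so endoscopy itself largely separates it from a tumour or ulcerative colitis. Separating it from other diarrhea in a normal-looking colon is harder. A single pooled contrast mixes the two questions. A reader who sees no difference in CRP cannot tell whether MC resembles normal-colon diarrhea on that marker, or whether it lies above normal-colon diarrhea and below organic disease so that the two cancel.

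At stake is how far the secondary objective of comparing MC with non-MC patients (section 3.2) can be interpreted. Section 2.3 wants the features that distinguish MC from other conditions, and one mixed group cannot say which conditions. Adjusting for age and sex would not help, because the matter is who is in the comparator.

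The histological part of the same objective adds a wrinkle. Section 4 ties specimen collection to macroscopically normal colonoscopies, although section 7.3 is worded more broadly. On the section 4 reading, non-MC would mean normal-colon patients in the histology rows and the pooled group in the clinical and laboratory rows.

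**Working it through.** **The plan's own figures.** Section 9.2 gives N = 300, prevalence 10-15% and a 95% margin below 4.5%. The Wald half-width is 1.96 × √[p(1 − p)/300].
- p = 0.10: 1.96 × √(0.09/300) = 0.0339.
- p = 0.15: 1.96 × √(0.1275/300) = 0.0404.

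Both are below 4.5%, so the stated margin reproduces. The expected counts are 300 × 0.10 = 30 MC and 270 non-MC, or 300 × 0.15 = 45 MC and 255 non-MC.

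**Effect of pooling.** Let f be the share of non-MC patients with organic disease, d the MC minus normal-colon difference, and D the organic minus normal-colon difference, both in SD units. None of these is in the documents. I assume d = 0.5, D = 1.0, 1.5 or 2.0, f = 10-30%, equal within-group SDs and a two-sided 0.05 test.

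- Pooled difference = d − fD
- Variance of the pooled non-MC group = 1 + f(1 − f)D²
- SE = √(1/30 + variance/270)
- Power = Φ(|difference|/SE − 1.96) + Φ(−|difference|/SE − 1.96)

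Worked case, D = 1.5 and f = 0.20:
- difference = 0.5 − 0.20 × 1.5 = 0.20
- variance = 1 + 0.16 × 2.25 = 1.36
- SE = √(0.03333 + 0.00504) = 0.196
- power = 0.18

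Difference in SD, with power in brackets, for 30 MC patients:

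| Comparator | f = 10% | f = 20% | f = 30% | Zero at f = d/D |
|---|---|---|---|---|
| Pooled, D = 1.0 | 0.40 (0.54) | 0.30 (0.34) | 0.20 (0.18) | 50% |
| Pooled, D = 1.5 | 0.35 (0.44) | 0.20 (0.18) | 0.05 (0.06) | 33% |
| Pooled, D = 2.0 | 0.30 (0.33) | 0.10 (0.08) | −0.10 (0.08) | 25% |
| Normal colon, negative histology only | 0.50 (0.73), n = 243 | 0.50 (0.73), n = 216 | 0.50 (0.72), n = 189 | none |

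With 45 MC patients the pattern is the same. At f = 10-20% the normal-colon contrast has power 0.86-0.87 and the pooled contrast 0.69 down to 0.09, depending on D.

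**Three readings of the table.**
- Attenuation appears already at 10-20% organic disease. The sign changes only above d/D, which is 25-50% here. That threshold belongs to the assumed ratio and would be lower for a smaller d relative to D.
- All of this supposes that MC and organic disease shift the variable the same way. If they shift it in opposite directions, pooling enlarges the difference: with D = −1.5 and f = 0.20 it becomes 0.5 + 0.30 = 0.80 SD.
- Restricting the comparator costs almost no power, because the 30 MC patients dominate the SE (1/30 = 0.033 against 1/216 = 0.005).

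**The case against.** The strongest reply is that the pooled comparator is what the protocol set out to use. Section 2.3 asks what distinguishes MC from other conditions among patients attending with chronic watery diarrhea, and a newly found tumour or colitis is such a condition. Laboratory values are taken before colonoscopy, when those patients still belong to the differential diagnosis. Restricting to normal colons conditions on a later test and changes the estimand. This stands. A reader might infer that the pooled contrast is biased or wrong, and the documents do not support that. The weakness is only that it is the sole contrast.

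Other stronger readings also fail:

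- **Findings will be reversed.** Reversal needs a large organic share, and section 6.3 already removes known intestinal disease.
- **The case mix is an accident of each site.** Section 4 requires consecutive enrolment, so the mix is meant to reflect the clinic population.
- **Abdominal pain and weight loss are affected endpoints.** Both are collected at baseline, but the MC versus non-MC list in section 8.2 names neither.
- **An alternative diagnosis is recorded for every patient.** In section 7.1 that item applies only to macroscopically normal colonoscopies. Abnormal ones have a result and a description.

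The normal-colon group is not homogeneous either: section 7.1 expects some of these patients to receive another diagnosis. The added contrast is cleaner with respect to visible disease, not pure.

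Finally, an analysis plan not shown might stratify. That is possible, but section 4 itself defines the pooled group and names no other.

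**Conclusion.** The point holds as a cheap improvement to a secondary, hypothesis-free comparison. The protocol states one contrast, against a mixed group, and that contrast cannot separate MC versus normal-colon diarrhea from MC versus organic disease. Under the stated assumptions (d = 0.5 SD, D = 1.0-2.0 SD, 30 versus 270), an organic share of 10-20% reduces the difference to between 0.40 and 0.10 SD and power from about 0.73 to between 0.54 and 0.08. These are illustrations: the documents give neither the organic share nor any effect size, and opposite shifts would exaggerate the difference instead. The pooled contrast remains legitimate as description. The primary prevalence endpoint is unaffected, since splitting the non-MC group changes neither its numerator nor its denominator.

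**What to change.** Keep the pooled comparison. In sections 4 and 8.2, add a prespecified comparison of MC patients with patients who have a macroscopically normal colonoscopy and negative histology. Show abnormal-colonoscopy patients in a separate column of the same table. The two-sample tests already in section 9.1 serve the added contrast.

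State beforehand which abnormal findings count as explanatory. Section 7.1 already asks the site to "describe whether other findings may have caused diarrhoea", and that item can carry the rule. Say also where patients with an abnormal but non-explanatory finding go.

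The cost is some wording, one table column and that classification rule. No new data item is needed, because the colonoscopy result and its description are recorded for all patients. The downsides are a somewhat smaller comparator (for example 216 instead of 270 at a 20% organic share), more exploratory comparisons, which should be labelled as such, and some judgement in applying the rule.
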